8.3. Manufacture and labeling of IMP

The sponsor supplies the investigational site with an approved and authorized medicinal product as commodities. Thus a labeling in accordance with § 5 of the GCP-Verordnung (GCP-V) [8] is not intended.

8.4. Storage, dispensing and return of IMP

The vial is kept in the packaging to protect from light and stored at room temperature.

The investigator must maintain accurate records accounting for the receipt and disposition of the IMP. Therefore, a preprinted drug dispensing log is provided to the site. This log must identify the patient and must be kept current. Furthermore, the amount of medication administered to each patient at each visit (with corresponding dates) must be documented on it. All medication supplies (empty containers, as well as partly used and unused medication) must be made available for inspection at every monitoring visit. Depending on local regulations all unused medication, partly used and empty packages can either be returned to the sponsor or destroyed at site. In any case the return or destruction must be documented accordingly.

8.5. Assignment of patients to treatment groups

This clinical trial is a single-group study.

8.6. Blinding and unblinding

Treatment in this clinical trial is open.

However, to minimize bias, a central ECG reader (cardiac specialist) will be blinded to the investigational site, patient data (patient ID, name, initials and birth date) and the time point on which the ECG was taken. In this way the blinded reader is not able to identify if the ECG was taken before (ECG-1), during (ECG-2) or after (ECG-3) the treatment with argatroban. In addition, automatically evaluated and printed ECG data (e.g. QT interval and diagnostic data) will be blackened in order to reduce any influence on the evaluation result provided by the blinded cardiac specialist.

Finally, each blinded ECG recording will be pseudonymized manually by adding a unique number. Therefore, a table with pseudonymization numbers will be provided to the site. The unique number identifies the investigational site, patient and the time of ECG measurement.

The process of blinded ECG assessment is defined as follows: The investigational site adds the respective pseudonymization number on the ECG record and sends the record to responsible personnel of the blinding team of the cardiology department of the [REDACTED], who rechecks the pseudonymization number and finally blackens the ECG record. The responsible personnel forwards the blackened and pseudonymized ECG record to a blinded cardiac specialist. The blinded cardiac specialist will provide her/his assessment in a timely manner by means of an evaluation sheet. The cardiac specialist forwards the evaluation sheet to the responsible personnel of the blinding team, who forwards the sheet to the respective investigational site and the data management of [REDACTED].

[REDACTED] will calculate the Δ QTc value. In case the QTc interval shows a prolongation of more than 500 ms during or after treatment or indicates an increase by more than 60 ms compared to baseline (ECG-1), [REDACTED] will inform the internal data monitoring committee and the sponsor so

that assessment of safety of the study can be done. In addition to this [REDACTED] will inform the responsible investigator of the respective site in case the QT interval prolonged by more than 60 ms compared to baseline value ($\Delta QTc > 60$ ms).

If the interpretation of QTc prolongation is unclear or associated with clinically relevant arrhythmias, an expert in cardiological electrophysiology at the respective center will be involved in interpreting the respective ECGs and to define further proceeding.

8.7. Previous and concomitant disease, medication and treatment

Diseases, any medications and treatments the patients received in the last 6 months prior to study start and during the study must be recorded in the case report form (CRF). A description of the type of drug or treatment, the drug amount, duration, reason for drug administration and outcome must also be documented.

Adverse events (AEs) related to the administration of a concomitant medication or the performance of a procedure not part of the routine PCI must also be documented on the appropriate AE page of the CRF.

The use of concomitant medication that interfere with the QTc interval is not allowed.

8.8. Rescue therapy for emergencies

Excessive anticoagulation can be controlled by stopping argatroban infusion or reducing infusion dose. A specific antidote does not exist. Treatment shall be done according to symptoms and medical indication.

8.9. Continuation of treatment after the end of the clinical trial

Treatment after the PCI procedure will be according to local clinical routine.

9. Premature termination

9.1. Withdrawal of patients

Patients have the right to withdraw from the study at any time for any reason. The investigator also has the right to withdraw patients from the study in the event of intercurrent illness, AEs and treatment failure, administrative reasons or other reasons. An excessive rate of withdrawals can render the study uninterpretable; therefore, unnecessary withdrawal of patients should be avoided. Should a patient decide to withdraw, all efforts will be made to complete and report the observations as thoroughly as possible. A complete final evaluation at the time of the patient's withdrawal should be made with an explanation of why the patient is withdrawing from the study. If the reason for removal of a patient from the study is an AE or an abnormal laboratory test result, the principal specific event or test will be recorded on the CRF.

9.2. Closure of trial sites

See "premature termination of trial".

9.3. Premature study termination

Both the sponsor and the principal coordinating investigator reserve the right to terminate the study at any time. Should this be necessary, both parties will arrange the procedures on an individual study basis after review and consultation. In terminating the study, the sponsor and the principal coordinating investigator will assure that adequate consideration is given to the protection of the patient's interests. The following criteria could lead to a discontinuation or early termination of the study:

- Negative benefit/risk assessment due to new information
- It is no longer ethical to continue treatment with the IMP
- It is no longer practicable to complete the trial
- The sponsor considers that the trial must be discontinued for safety reasons (e.g. after occurring of an increase in QT/QTc > 500 ms or of > 60 ms over baseline in a number of $\geq 30\%$ patients)
- Business considerations

In case of premature study termination all collected data must be analysed and a report has to be written. The sponsor has to inform the responsible regulatory authority and the responsible ethics committee within 15 days, giving detailed reason for the premature termination.

10. Study assessments, efficacy and safety variables

10.1. Clinical and laboratory assessments

The following assessments will be collected and documented accordingly in the CRF:

Screening:

- Informed consent
- Inclusion and exclusion criteria
- Age, gender, ethnicity, height, bodyweight
- Vital signs (resting pulse rate, systolic and diastolic blood pressure measured in a sitting position)
- Information on coronary artery disease
- Pregnancy test (urine)
- Hemogram (containing leucocytes, thrombocytes, hemoglobin, hematocrit)
- Liver function profile (bilirubin, AST/SGOT, ALT/SGPT, γ GT)
- Kidney function profile (serum creatinine, GFR)
- Hs-Troponin-T
- Electrolytes (Na, K, Ca)
- Coagulation status (INR, aPTT)
- 12-lead ECG-1

- Relevant medical history and current medical conditions
- Previous and concomitant medication
- Previous treatment (non-drug therapy) related to cardiac disease

Treatment:

- Duration of PCI
- Coagulation status (ACT)
- Hematocrit (only if clinically necessary)
- 12-lead ECG-2
- Information on concomitant drug treatment
- Adverse Events

Follow-up:

- Coagulation status: ACT and dTT (for assessment of argatroban plasma concentration)
- Hematocrit
- 12-lead ECG-3
- Information on concomitant treatment (drug and non-drug therapy)
- Adverse Events

10.2. Primary target variable

QTc interval:

The QT interval represents the duration of ventricular depolarization and subsequent repolarization and is measured from the beginning of the QRS complex to the end of the T wave. Reading of ECG data including the calculation of QT interval will be done automatically by use of the ECG machine Mac 5500, GE Healthcare supplemented by manual reading in any case.

Measurement of QT time will be done according to recommendations published by Goldenberg et al. [9]. This also includes tracing at 25 mm/s paper speed at 10 mm/mV amplitude for an accurate measurement of QT interval duration. In addition, QT interval will be determined as a mean value derived from the least 3-5 cardiac cycles (heart beats), and is measured from the beginning of the earliest onset of the QRS complex to the end of the T wave. The QT measurement is made in leads II and V5 or V6, the longest value will be used [9].

Because of its inverse relationship to heart rate, measured QT interval will be routinely corrected by a formula to a less heart rate dependent value known as the QTc interval:

$$\text{Bazett's correction: } \text{QTc} = \text{QT}/\text{RR}^{0.5}$$

The RR interval is the interval between two R-waves in the ECG.

To answer the primary endpoint, QTc interval will be determined by 12-lead ECG at following time points:

- Prior to first bolus dose of argatroban (baseline ECG/ ECG-1)

- Immediately after cardiac intervention when patient is under full anticoagulation with argatroban (ECG-2)

All ECGs measurements will be forwarded to an ECG reader, a cardiac specialist, blinded to time, treatment and patient identifier. Therefore, each ECG will get a random number identifying the patient and timing of PCI.

10.3. Secondary target variables

QTc interval:

To answer the secondary endpoint, QTc interval will be determined by 12-lead ECG at following time point:

- > 8 but ≤ 28 hours after termination of infusion of argatroban maintenance dose (ECG-3)

10.4. Other variables

ACT:

Blood samples for the assessment of anticoagulation level will be obtained from patients as described in section 6.3.

Plasma samples will be obtained from patients at 5 min after completion of the initial bolus of argatroban and at 5 min after completion of every further bolus until target ACT range is reached. A final ACT measurement is planned > 8 but ≤ 28 hours after PCI. Further ACT assessments are possible but depend on clinically relevancy (e.g. in case of prolonged PCI procedure).

The final ACT measurement > 8 but ≤ 28 hours is to be conducted as part of the follow-up procedure in order to evaluate whether the pharmacodynamic effect of argatroban faded off completely. This status is indicated by an ACT value of ≤ 160 s. If clinically indicated, further ACT assessments can take place.

10.5. Bleedings

The incidence of hemorrhagic events during the PCI must be categorized according to the definition of CABG-related bleeding [10]:

Type 0	No bleeding
Type 1	Bleeding that is not actionable and does not cause the patient to seek treatment
Type 2	Any clinically overt sign of hemorrhage that "is actionable" and requires diagnostic studies, hospitalization, or treatment by a health care professional
Type 3	
 a. Overt bleeding plus hemoglobin drop of 3 to < 5 g/dL (provided hemoglobin drop is related to bleed); transfusion with overt bleeding b. Overt bleeding plus hemoglobin drop ≥ 5 g/dL (provided hemoglobin drop is related to bleed); cardiac tamponade; bleeding requiring surgical intervention for control; bleeding requiring IV vasoactive agents c. Intracranial hemorrhage confirmed by autopsy, imaging, or lumbar puncture; intraocular bleed compromising vision

Type 4	CABG-related bleeding within 48 hours
Type 5	
 Probable fatal bleeding Definite fatal bleeding (overt or autopsy or imaging confirmation)

10.6. Adverse events and adverse drug reactions

The summary of product characteristics (SmPC) will be used as reference document for study medication and will be provided to the investigators.

It is the responsibility of investigator(s) to report all AEs in the CRF. Any serious adverse event (SAE) must be reported to the sponsor within one working day.

10.6.1. Adverse event (AE)

An AE is any untoward medical occurrence in a patient administered an IMP. There does not necessarily have to be a causal relationship with this treatment.

An AE can therefore be any unfavorable and unintended sign (including an abnormal laboratory or ECG finding, for example), symptom, or disease temporally associated with the use of a medicinal product, whether or not considered related to the medicinal product. Pre-existing conditions which worsen during a study are to be reported as AEs. They can become SAEs if they fulfill one of the seriousness criteria described in section 10.6.2.

All AEs encountered during the clinical study will be reported on the AE page of the CRF. Reporting of new AEs starts at the beginning of the study (date of treatment visit) and ends at study termination (after completion of ECG-3 measurement).

AEs of special interest are cardiac (e.g. arrhythmic) events. For that reason, each abnormal ECG finding (e.g. morphological abnormality like prolonged QT/QTc interval) must be handled and respectively documented as AE. An evaluated QT/QTc interval is categorized as "prolonged" if the following limit is reached: **Absolute QTc interval prolongation: QTc interval > 450 ms.**

Severity of AEs will be graded 1 through 3 and reported in detail as indicated on the CRF:

- Grade 1, Mild; asymptomatic or mild symptoms; clinical or diagnostic observations only; intervention not indicated.
- Grade 2, Moderate; minimal, local or noninvasive intervention indicated; limiting age-appropriate daily activity.
- Grade 3, Severe or medically significant but not immediately life-threatening; hospitalization or prolongation of hospitalization indicated; disabling; limiting self-care, Inability to work or perform normal daily activity.

Relationship of the AE to treatment should also be assessed. Description of scales can be found in section 10.6.5.

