5.5. Secondary endpoints

- Mean difference in QTc interval between ECG-3 and ECG-1.
- Proportion of patients with a prolongation of QTc interval to > 500 ms at ECG-2.
- Proportion of patients with a prolongation of QTc interval to > 500 ms at ECG-3.
- Proportion of patients with a prolongation of QTc interval of > 60 ms at ECG-2 compared to ECG-1.
- Proportion of patients with a prolongation of QTc interval of > 60 ms at ECG-3 compared to ECG-1.
- Incidence of haemorrhagic events according to the definition of CABG-related bleeding.
- Incidence of adverse events.

6. Trial conduct

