7.3. Exclusion criteria

Patients with any of the following exclusion criteria will not be eligible for participation:

General exclusion criteria:

- Patient is indicated for highly complex 3-vessel intervention.
- The female patient is pregnant (exclusion by routine urine test) or is nursing during therapy period.
- Patients who are currently participating in another clinical trial or patients who participated in another clinical trial during the last 3 months prior to study start (date of treatment visit).
- History of drug, alcohol or chemical abuse within 6 months prior to study start.
- Planned surgical intervention other than study procedure within 7 days after study start.
- Any condition, which contraindicates the use of argatroban, or endangers the patient if he/she participated in this study.

Factors influencing QTc interval:

- Marked baseline prolongation of QTc interval (repeated demonstration of a QTc interval > 450 ms at baseline ECG).
- A history of risk factors of Torsade de pointes (e.g. heart failure, hypokalemia, family history of Long QT Syndrome).
- Known intraventricular conduction disturbance.
- Bradycardia: heart rate < 45 min⁻¹.
- Electrolyte level outside normal range (according to laboratory's reference values).
- The use of concomitant medications that interfere with the QTc interval.

- Intake of digitalis within the last 2 weeks before study start.
- Acute myocardial infarction or troponin-positive unstable angina.

Factors inhibiting use of argatroban in this study:

- Intolerance to ingredients of Argatra® (sorbitol).
- Known cirrhosis, hepatitis, clinically significant hepatic disorder at study start and/or history of clinically relevant hepatic disorder.
- Current hepatic disorder indicated by laboratory liver profile at screening: Bilirubin, AST/SGOT, ALT/SGPT, γ GT > 3.0 times upper limit of the normal (ULN).
- Renal insufficiency indicated by laboratory renal profile at study start: GFR < 35 ml/min.
- Uncontrolled hypertension (defined as blood pressure >180/120 mmHg).
- If any form of heparin was taken prior to study start and aPTT \geq 35 s.
- Intake of direct oral anticoagulants (DOAC) within 1 month prior to study start.
- If anticoagulants of type of vitamin K antagonists (VKA) were taken prior to study start and INR >1.2.
- Platelet count <125 \times 10⁹/l.
- Documented coagulation disorder or bleeding diathesis.
- Uncontrolled haemorrhage within the past 3 months.

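### The ECG adverse-event rule in Protocol 10.6.1 ignores ECG-1: taken literally it counts unchanged findings as adverse events, and it is not aligned with the > 60 ms change criterion

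*Protocol*

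**What the plan says.** Protocol section 10.6.1 contains four statements that bear on the point.

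- The class of special interest is broad: "AEs of special interest are cardiac (e.g. arrhythmic) events", which goes well beyond QTc.
- The section then draws a reporting rule from this, namely that "each abnormal ECG finding (e.g. morphological abnormality like prolonged QT/QTc interval) must be handled and respectively documented as AE". The limit for prolonged is given as "Absolute QTc interval prolongation: QTc interval > 450 ms".
- On timing: "Reporting of new AEs starts at the beginning of the study (date of treatment visit". ECG-1 is recorded at screening, before that window opens.
- On existing disease: "Pre-existing conditions which worsen during a study are to be reported as AEs".

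Three other places use QTc limits. Section 7.3 excludes a patient only on "repeated demonstration of a QTc interval > 450 ms at baseline ECG". Section 8.6 sends an alert to the internal data monitoring committee, the sponsor and the investigator when QTc "indicates an increase by more than 60 ms compared to baseline (ECG-1". Section 5.5 has the matching endpoint, "Proportion of patients with a prolongation of QTc interval of > 60 ms at ECG-2 compared to ECG-1", and the same for ECG-3. Section 9.3 uses the > 60 ms rise in an example of a reason to stop the trial.

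Incidence of adverse events is a secondary endpoint in Protocol 5.5 and a safety endpoint in SAP 12.3. SAP 15.6.1 tabulates adverse events by MedDRA term, with a separate analysis of related events, and gives no rule for QTc-based events.

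**The concern.** The ECG sentence and the 450 ms limit look only at the current tracing. Elsewhere the trial judges QTc by comparison with ECG-1: in the primary endpoint, the > 60 ms endpoints and the alert.

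A site that follows the ECG sentence as written would record a finding that was there before the drug was given. Because ECG-1 lies outside the reporting window, ECG-2 is the first study tracing on which an old finding can be logged, so it would look like an event with onset on the treatment day. Another site, relying on the sentences about new events and worsening, would not record it. The section does not say which instruction takes precedence.

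At stake is the ECG part of a named endpoint, in a trial whose purpose is to supply QTc safety data. With a single group there is no comparator to show how many such events are background.

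**Working it through.** **Step 1: apply the rules to the same tracings.** The QTc values are illustrative.

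| Case | ECG-1 | ECG-2 | Change | ECG rule of 10.6.1, literal | New / worsen sentences of 10.6.1 | > 60 ms criterion |
|---|---|---|---|---|---|---|
| A | old abnormality | same abnormality | none | AE | not an AE | not applicable |
| B | 455 ms, one reading | 452 ms | 452 − 455 = −3 ms | AE | not an AE | no |
| C | 449 ms | 451 ms | 451 − 449 = +2 ms | AE | AE (newly above the limit) | no |
| D | 385 ms | 448 ms | 448 − 385 = +63 ms | not prolonged | left open | yes: alert and endpoint |

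Case B can enter the trial because section 7.3 requires a repeated value and the schedule lists one screening ECG. Cases A and B are the conflict inside section 10.6.1. Case C is not: QTc rose and newly crossed the limit. Case D is the mismatch with sections 5.5, 8.6 and 9.3.

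**Step 2: when case D is possible.** QTc2 = QTc1 + ΔQTc. If ΔQTc > 60 and QTc2 ≤ 450, then QTc1 < 450 − 60 = 390 ms.

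**Step 3: how often case D could occur.** The documents state no SD for ΔQTc, but Protocol Table 1 implies one. For the one-sided one-sample t-test with n = 45 and alpha 5%, the noncentrality is (10 − μ)·√45 / SD on 44 degrees of freedom. With SD = 10 and μ = 6 it is 4 × 6.708 / 10 = 2.68, and the power is 0.841, as printed. Solving the rows for μ = 4 to 8 gives SDs of 9.98 to 10.01, so the planning SD is 10 ms.

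- SD 10 ms, mean change 0: z = 60/10 = 6, P(ΔQTc > 60) ≈ 1 × 10⁻⁹.
- SD 10 ms, mean change 10: z = 50/10 = 5, P ≈ 3 × 10⁻⁷.
- SD 30 ms (assumed, three times the planning value), mean change 0 to 10: z = 2.00 to 1.67, P ≈ 2.3% to 4.8%.

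In that last setting, also assume QTc1 is normal with mean 400 to 430 ms and SD 15 to 20 ms, cut at 450 ms. Then 0.1% to 17% of the rises end at or below 450 ms. The largest expected number is 50 × 0.0478 × 0.1611 ≈ 0.4 patients in 50 at ECG-2.

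**Step 4: cases A and B.** Their number depends on how many patients bring old ECG abnormalities and how many have a single screening QTc above 450 ms. The documents give neither, so the direction is clear (upward) but the count is not.

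**The case against.** The best defence is that section 10.6.1 already contains the limit. An unchanged old finding is neither new nor worse, so a careful investigator would not record it. Section 7.3 also removes repeated QTc above 450 ms and known intraventricular conduction disturbance. Part of this stands: the sensible reading is available, and the exclusions narrow the problem. But the ECG sentence says each finding must be documented, is introduced as a special provision for the events of special interest, and carries no exception. Two sites can each claim to follow the protocol and record differently.

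It is also fair to say that an absolute limit is a cautious reporting choice, and that SAP 15.5.1 lists QTc1, QTc2 and QTc3 for every patient. A reader could therefore sort out the QTc cases by hand. The adverse-event table itself would still mix them.

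Four stronger readings are tempting, and the documents do not support them.

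- *The trial misreports its event of special interest.* That event is cardiac events in general, of which QTc above 450 ms is only one part.
- *Rises above 60 ms are missed.* They can lose only the prolonged label. They remain two secondary endpoints and an alert, and the open-ended wording of the ECG sentence lets an investigator record them anyway.
- *The adverse-event table and the > 60 ms endpoint contradict each other.* Different criteria give different counts, which is not a contradiction.
- *Several false events can be predicted.* One can simulate chance crossings of 450 ms. Assume no drug effect, QTc mean 410 to 430 ms, between-patient SD 15 to 20 ms, paired SD 10 to 15 ms and entry at or below 450 ms. Then 0.9% to 14.2% of patients, or 0.4 to 6.4 of 45, exceed the limit at ECG-2 or ECG-3. But all of them start at or below 450 ms, so they are case C: new crossings, properly recordable under either reading. The figure does not measure the unchanged findings at issue.

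**Conclusion.** The point holds as an inconsistency in reporting rules that should be corrected. The ECG rule of section 10.6.1, taken literally, turns unchanged findings into adverse events, conflicts with two other sentences of its own section, and pushes the ECG part of adverse-event incidence upward with no control arm to reveal it. It is also not aligned with the > 60 ms criterion. That second gap exists only for QTc1 below 390 ms. It is practically nil at the planning SD of 10 ms, and at most about 0.4 patients in 50 at ECG-2 under the assumed SD of 30 ms and the assumed QTc1 ranges.

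The size of the over-recording cannot be stated from the documents. The primary test and the secondary QTc endpoints do not use the adverse-event rule and are unaffected.

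**What to change.** Reconcile Protocol sections 7.3, 8.6 and 10.6.1:

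- Record an ECG finding as an adverse event only if it is new or worse than on ECG-1, and say how a single baseline QTc above 450 ms is treated under that rule.
- State how a rise above 60 ms that triggers the section 8.6 alert is handled as an adverse event when QTc ends at or below 450 ms.
- State whether the investigator's or the blinded reader's value decides. SAP 15.5.1 presents both interpretations, and neither document says which one makes the adverse event.

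In SAP 15.6.1, tabulate QTc-based adverse events together with QTc1 and the change from ECG-1. Borderline crossings such as 449 to 451 ms remain adverse events under this wording, and the table lets a reader tell them from real rises.

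The cost is wording in both documents. All ECG values are already collected, so no new data are needed. The downside is that some ECG adverse events already recorded would be reclassified, which the study report should disclose.
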